8.7.2 Sample Size and Power for Efficacy Analyses

Approximately 600 subjects in the ITT population (randomized and treated) will be enrolled in this study and randomly assigned to receive either POS monotherapy or VOR monotherapy in a 1:1 ratio. This study (with approximately 300 ITT population in each azole monotherapy arm) will have ~> 80% power (with 1-sided alpha=0.025) to show non-inferiority of POS monotherapy compared to VOR monotherapy using a 10% margin and assuming a mortality rate through Day 42 of 23% for VOR treated subjects (based on the estimated historical VOR all-cause mortality rate through Day 42 shown in [Table 17](#) [25, 27]).

[Table 17](#) summarizes the study power for assumed VOR mortality rates ranging between 18% and 28%, for different number of subjects in each arm, with the POS mortality rate ranging from -2% to +2% from the VOR rate.

- For example, if the VOR mortality is assumed to be 18% and the POS mortality is assumed to be 19% with 600 subjects (300/arm) in ITT population, then this study design has 80.4% power to demonstrate non-inferiority with a 10% margin.
- Alternatively, if the VOR mortality is assumed to be 22% and the POS mortality is assumed to be 21% with 540 subjects (270/arm), then this study design has 87.2% power to demonstrate non-inferiority with a 10% margin.

Table 17 Power (%) Under Various Assumptions of All-cause Mortality Through 42 days (10% Non-inferiority Margin)

Underlying All-cause Mortality Through 42 days for VOR (%)	Underlying Difference in Mortality (%) (POS minus VOR)				
	-2.0	-1.0	0.0	1.0	2.0
600 subjects (300/arm)					
18%	97.2%	94.0%	88.5%	80.4%	69.9%
19%	96.7%	93.1%	87.3%	79.0%	68.4%
20%	96.1%	92.2%	86.1%	77.5%	66.9%
21%	95.5%	91.3%	84.9%	76.2%	65.5%
22%	94.8%	90.4%	83.8%	74.9%	64.2%
23%	94.2%	89.5%	82.7%	73.7%	63.0%
24%	93.6%	88.6%	81.6%	72.5%	61.8%
570 subjects (285/arm)					
18%	96.5%	92.8%	86.9%	78.4%	67.7%
19%	95.9%	91.9%	85.6%	76.9%	66.2%
20%	95.2%	90.8%	84.3%	75.4%	64.6%
21%	94.5%	89.9%	83.1%	74.1%	63.3%
22%	93.8%	88.9%	81.9%	72.7%	61.9%
23%	93.1%	88.0%	80.8%	71.5%	60.8%
24%	92.4%	87.0%	79.6%	70.3%	59.6%
540 subjects (270/arm)					
18%	95.6%	91.5%	85.0%	76.2%	65.3%
19%	94.9%	90.4%	83.7%	74.7%	63.8%
20%	94.1%	89.3%	82.3%	73.1%	62.3%
21%	93.4%	88.3%	81.0%	71.8%	61.0%
22%	92.6%	87.2%	79.8%	70.4%	59.6%
23%	91.8%	86.2%	78.6%	69.2%	58.5%
24%	91.0%	85.2%	77.4%	68.0%	57.3%

Note: The power is calculated based on a non-inferiority margin of 10% and $\alpha=0.025$ (one-sided).

In terms of observed mortality rates that would meet the non-inferiority criteria, if an all-cause mortality rate of 23% is observed in the 300 VOR patients (23%=69/300), the largest observed all-cause mortality rate that could be observed among POS patients and still meet the non-inferiority criterion would be 26% (78/300). In this instance, the observed difference in mortality rates would be 3.0 percentage points (POS minus VOR) with a 95% CI of (-3.9, 9.9).

If an all-cause mortality rate of 23% is observed in 270 VOR patients (23%=62/270), the largest observed all-cause mortality rate that could be observed among POS patients and still meet the non-inferiority criterion would be 26% (69/270). In this instance, the observed difference in mortality rates would be again 3.0 percentage points (POS minus VOR) with a 95% CI of (-4.7, 9.8).

If the criteria for non-inferiority are met, then a superiority analysis of POS arm will be assessed.

8.7.3 Sample Size and Power for Safety Analyses

The safety hypotheses will be assessed by review of the accumulated safety data. Table 18 gives the difference in percentage points (POS minus VOR) that can be ruled out with different power levels and 95% confidence when there are 300 or 285 or 270 randomized subjects in each treatment group. The true frequency of subjects experiencing an AE on POS arm is assumed the same as that in the VOR arm. For a reasonably common adverse experience which occurs in 20% of subjects receiving either POS or VOR, the study with 300 randomized subjects in each arm has 90% power to declare, with 95% confidence that the true difference between group proportions is no more than 12.7 percentage points.

If a particular AE is not observed from the 300 randomized subjects receiving POS, it can be ruled with 2-sided 95% confidence interval that the upper limit of the true occurrence of this AE is no more than 1.8 percentage points.

Table 18 Difference in AE Proportions (POS minus VOR)† That Can Be Ruled Out With Different Number of Randomized Subjects in Each Group.

Target Power	Difference in Percentage Points that can be Ruled Out with Target Power when True AE Occurrence is				
	10%	20%	30%	40%	50%
600 subjects (300/arm)					
80%	8.8	11.0	12.1	12.5	12.5
85%	9.4	11.7	12.9	13.3	13.2
90%	10.3	12.7	13.9	14.3	14.2
95%	11.5	14.1	15.3	15.8	15.6
570 subjects (285/arm)					
80%	9.1	11.3	12.4	12.9	12.8
85%	9.7	12.0	13.2	13.7	13.6
90%	10.6	13.0	14.2	14.7	14.6
95%	11.9	14.4	15.7	16.2	16.0
540 subjects (270/arm)					
80%	9.4	11.6	12.8	13.2	13.1
85%	10.1	12.4	13.6	14.0	13.9
90%	10.9	13.4	14.6	15.1	14.9
95%	12.2	14.8	16.2	16.6	16.4

†The upper bound of the two-sided 95% confidence interval [21] for the difference in AE incidences (POS minus VOR) assuming the incidences are the same.

8.8 Subgroup Analyses and Effect of Baseline Factors

To determine whether the treatment effect is consistent across various subgroups, the estimate of the between-group treatment effect (with a nominal 95% CI) for the primary endpoint will be estimated and plotted within each category of the following classification variables:

- Region (US, Ex-US)
- Sex (female, male)
- Age among adults (≥ 18 years to \leq median of adults, $>$ median of adults)
- Ethnic Origin (Black, White, Other) and (Hispanic, Non-Hispanic)
- Risk status for mortality/poor outcome (high risk, not high risk).
- Patients population: (1) proven vs. probable IA; (2) site of IA infection (lung, sinus, multiple sites, etc.); (3) underlying disease; (4) neutropenic status at baseline (ANC < 500 vs. > 500)

The consistency of the treatment effect will be assessed descriptively via summary statistics by category for the classification variables listed above.

8.9 Interim Analyses

There is no formal interim analysis planned for this study.

A formal independent external Data Monitoring Committee (eDMC) will be assembled at the onset of the study and will examine data for safety. The eDMC will monitor safety and provide recommendations to the executive committee of the SPONSOR. The executive committee, composed of the SPONSOR Senior Management, will provide the overall scientific direction for the trial, and will receive and decide on any recommendations made by the eDMC regarding interrupting enrollment due to safety issues or early stopping of the study. Details regarding the eDMC will be described in External Data Monitoring Committee Charter.

8.10 Compliance (Medication Adherence)

In this study, as part of the routine recording of the amount of study treatment taken by each patient, at each site, the volume of infusion administered, and the number of tablets/capsules dispensed and returned will be counted, reviewed, and recorded at regular intervals at the local level. Pharmacy records of dispensing and return of study medication will be recorded using local documentation records and will be monitored and reviewed by un-blinded study monitors throughout the study period. Pharmacy records will be retained at the local pharmacy and available for Sponsor

review. Site records will be used to ensure and document study medication compliance. Study medication daily dosing will be recorded in the electronic case report for each study medication component (IV or oral, placebo or active drug) based upon local documentation records.

For IV study therapy, on each day, each patient should take a certain infusions/injections dosage encompassing both the assigned treatment and any matching placebo (sham infusions). A day within the study will be considered an “On-therapy” day if the patient receives at least one infusion.

For oral therapy, on each day, each patient should take a certain number of tablets and capsules encompassing both the assigned treatment and any dummy placebo tablets or capsules. A day within the study will be considered an “On-Therapy” day if the patient takes one capsules/tablet.

For a patient who is followed for the entire study period, the “Number of Days Should be on Therapy” is the total number of days from randomization to the last scheduled day for treatment administration for that patient. The compliance rate for each patient will be computed as follows:

$$\text{Percent Compliance} = \frac{\text{Number of Days on Therapy}}{\text{Number of Days Should be on Therapy}} \times 100.$$

Summary statistics will be provided on percent compliance by treatment group.

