7.4.1.3.2 Determining the Timing of Dose Administration for Each Subject

7.4.1.3.2.1 Posaconazole

[Table 4](#) provides what subjects randomized to the POS arm will receive when on IV therapy.

Table 4 Summary of POS IV Therapy

	Day 1 Dose	Day 2-84 Dose	Day 2-84 Dose for subjects with hepatic impairment
Drug	POS 300 mg twice a day	POS 300 mg first dose, placebo infusion second dose	POS 300 mg first dose, placebo infusion second dose
Volume	200 mL	150 mL	150 mL
Infusion rate	100 mL/hr	100 mL/hr	100 mL/hr
Infusion Duration	2 hr	1.5 hr	1.5 hr

[Table 5](#) provides what subjects randomized to the POS arm will receive when on oral therapy.

Table 5 Summary of POS Tablet Therapy

	Daily Oral Dose 300mg QD ^a	Daily Oral Dose for subjects with hepatic impairment 300mg QD
First Dose	2 orange VOR capsule placebos 3 yellow POS tablets	1 orange VOR capsule placebos 3 yellow POS tablets
Second Dose	2 orange VOR capsule placebos	1 orange VOR capsule placebos

^a If the subject starts on Day 1 with POS Tablet, they will receive 300 mg BID. The first dose should be: 3 orange VOR capsule placebos, and 3 yellow POS tablets. The second dose should be: 3 orange VOR capsule placebos, and 3 yellow POS tablets.

7.4.1.3.2.1.1 POS IV Solution

Subjects will have their IV infusions begun at the same time each day and are not to be administered until after the collection of the specified blood samples ([Section 7.6](#)).

POS IV will be given every 12 hours on the first day, with infusions being not less than 10 hours or no more than 14 hours apart. The subsequent POS IV infusions will be administered once daily 24 hours (\pm 2 hours) apart, in order to control one

source of variability in drug levels. Subjects who are randomized to POS will also receive a placebo infusion of 5% dextrose in water to make the number of infusions per day (2) similar for both treatment arms. Subjects will receive an IV infusion (POS or placebo) every 12 hours.

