8.11 Extent of Exposure

In addition, the Extent of Exposure to study treatment will be evaluated by summary statistics (N, mean, median, standard deviation) and frequencies for the “Number of Days on Therapy” by treatment group.

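### Section 8.10 counts placebo units towards an on-therapy day, so the descriptive compliance and exposure summaries can overstate receipt of the assigned azole; one Tier 2 sentence in 8.5.2 also needs aligning

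*Combined protocol and SAP*

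**What the plan says.** Section 8.10 describes the daily IV regimen as "encompassing both the assigned treatment and any matching placebo (sham infusions") and the daily oral regimen as "encompassing both the assigned treatment and any dummy placebo tablets or capsules". An IV day is an on-therapy "day if the patient receives at least one infusion"; an oral day is an on-therapy "day if the patient takes one capsules/tablet". Neither rule asks for active drug or for a minimum share of the day's units. Percent compliance is days on therapy divided by days that should be on therapy, summarised by arm. The denominator is defined only for a subject followed for the whole study. Section 8.11 uses the same numerator: "the Extent of Exposure to study treatment will be evaluated by summary statistics" and frequencies of the number of days on therapy.

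The regimen is in Section 7.4.1.3.2. From Day 2 the posaconazole IV day is "POS 300 mg first dose, placebo infusion second dose" (Table 4). The posaconazole oral first dose is "2 orange VOR capsule placebos 3 yellow POS tablets", and the second is placebo capsules only (Table 5). In the voriconazole arm both daily infusions (Table 6) and both daily capsule doses (Table 7) are active.

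Section 8.10 also says that dosing is recorded "for each study medication component (IV or oral, placebo or active drug").

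On Tier 2 safety events, Section 8.3.2, the main rule in 8.5.2 and Table 14 all require four or more subjects in any one arm. A later sentence in 8.5.2, about other categories such as system organ classes and predefined limits of change, refers instead to counts above four in both arms.

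**The concern.** A compliance or exposure table is normally read as showing how much of the assigned drug subjects received. Here a day can be credited to the posaconazole arm with no posaconazole taken. A voriconazole day is credited in full on one of two active doses, and an oral day of dummies alone counts in either arm. In a non-inferiority trial readers use these tables to judge whether under-dosing could have made the arms look alike, so a measure that hides partly dosed days gives false reassurance.

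The Tier 2 sentence raises a smaller issue. Taken as the only condition, it would withhold a between-arm interval from the most one-sided safety categories.

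**Working it through.** **1. Units on a maintenance day (Tables 4 to 7, standard schedule, from Day 2)**

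| Regimen | Units per day | Active | Placebo | Least active drug on a scored day |
|---|---|---|---|---|
| POS IV | 2 | 1 | 1 | 0 of 1 |
| VOR IV | 2 | 2 | 0 | 1 of 2 |
| POS oral | 7 | 3 | 4 | 0 of 3 |
| VOR oral | 7 | 4 | 3 | 0 of 4 |

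One oral unit is 1/7 = 14.3% of the day's units and scores the whole day. This part needs no assumption about missed doses.

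**2. Size if whole slots are missed.** The plan states no compliance figure to reproduce and no missed-dose rate. Assume that each of the two daily slots is missed as a whole with probability p, and that the two misses have correlation r.

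- P(both missed) = p² + r·p(1−p), so 8.10 reports 1 − p² − r·p(1−p) in both arms.
- Percentage of scheduled active doses taken = 1 − p in both arms.
- Excess = p(1−p)(1−r) in both arms.

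| p | r = 0 | r = 0.5 | r = 0.9 | r = 1 (whole days missed) |
|---|---|---|---|---|
| 2% | 2.0 | 1.0 | 0.2 | 0 |
| 5% | 4.8 | 2.4 | 0.5 | 0 |
| 10% | 9.0 | 4.5 | 0.9 | 0 |

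The entries are percentage points. Example: 0.05 × 0.95 × 1 = 0.0475.

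Measured instead as days with any active drug, the same excess applies to POS and is zero for VOR, because either VOR slot contains active drug. For a POS subject scheduled for all 83 days from Day 2 to Day 84, p = 5% gives 83 × 0.0475 = 3.9 days at r = 0, 2.0 at r = 0.5 and 0.4 at r = 0.9. At p = 10% it gives 7.5, 3.7 and 0.7 days. These are ceilings, since subjects who die or stop earlier have fewer scheduled days.

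**3. Size if single oral components are missed.** The formula in step 2 does not cover this case. Suppose the tablets and the two capsule doses are each missed independently with p = 10%.

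- 8.10 reports 1 − 0.1³ = 99.9% in both arms.
- Days with any active drug: POS 90.0%, an excess of 9.9 points; VOR 1 − 0.1² = 99.0%, an excess of 0.9 points.

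So the zero for VOR in step 2 holds only when whole slots are missed.

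**4. Tier 2 threshold.** Section 8.5.2 justifies the figure of four by saying that the interval covers zero when both equal-sized arms have fewer than four events. The unstratified Miettinen-Nurminen interval (Appendix 7), at 300 per arm, agrees: 3 v 0 gives −0.27 to 2.90 points and 4 v 0 gives 0.06 to 3.38. The same method returns the plan's own interval for 78/300 v 69/300, −3.9 to 9.9 (Section 8.7.2). Splits that qualify under the main rule but not under the later sentence, with one event per subject, are:

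| Split | 300 per arm | 270 per arm |
|---|---|---|
| 10 v 0 | 1.8 to 6.0 | 2.0 to 6.7 |
| 20 v 4 | 2.4 to 8.9 | 2.7 to 9.9 |

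**The case against.** Sections 8.10 and 8.11 are descriptive. No test, per-protocol set or decision depends on them, and the day rule is identical in both arms. Actual receipt is captured elsewhere: infusion volumes and unit counts (7.4.1.5.8), the date and reason for each noncompliance (7.4.3), missed doses (7.4.1.3.2) and trough concentrations (7.6, 7.7.4). Section 7.4.1.3.2 also says that no IV dose should be missed, so a small p is the more plausible case during IV treatment. Whole-day interruptions of the kind allowed in 7.7.2.6.2 produce no excess. All of this stands, and it keeps the severity low. It does not remove the point, because none of those records enters the 8.10 or 8.11 calculation.

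Three stronger readings are tempting, and the documents support none of them.

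- That compliance will be overstated. Without a missed-dose rate, only *can be* is supported; with full dosing the excess is zero.
- That the rule favours posaconazole. On percentage of active doses, the whole-slot model gives the same excess in both arms. The imbalance appears only on days with any active drug, where a once-daily and a twice-daily regimen differ even with identical dose-taking.
- That one-sided safety categories will lose their intervals. The later 8.5.2 sentence says that an interval will also be given, which adds a case and excludes none. Section 8.3.2, the main rule in 8.5.2 and Table 14 already state the intended threshold.

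**Conclusion.** The point holds at low severity. The 8.10 rule, reused in 8.11, can overstate receipt of the assigned azole on partly dosed days and cannot understate it. That follows directly from Tables 4 to 7. The size rests on assumed miss patterns: for whole-slot misses at p between 2% and 10%, the excess over percentage of active doses runs from 0.2 points (r = 0.9) to 9.0 points (r = 0) in both arms. It is zero for whole-day misses, and differs when single oral components are missed.

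A reader might infer that the primary non-inferiority result is at risk. It is not: the ITT mortality analysis and every analysis population are defined without reference to percent compliance or days on therapy.

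The Tier 2 inconsistency is real but editorial.

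**What to change.** **Compliance (8.10).** After unblinding, compute percent compliance from the component-level eCRF data as active doses of the assigned azole taken, divided by active doses scheduled. For subjects who do not complete, run the denominator to death or permanent discontinuation of study drug, which 8.10 leaves undefined. Use this measure to compare the arms.

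**Exposure (8.11).** Report days with at least one active unit within each arm, with a footnote that the count is not comparable between a once-daily and a twice-daily regimen. With whole-slot misses at p = 10% and r = 0, identical dose-taking gives 90% of days for POS and 99% for VOR.

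**Tier 2 (8.5.2).** Reword the later sentence to the threshold used in 8.3.2, the main 8.5.2 rule and Table 14: four or more subjects in any one arm.

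**Cost.** One derivation rule with its denominator, one footnote and one phrase. No new data are needed, and Section 8.0 allows changes to non-confirmatory analyses to be listed with reasons in the clinical study report. The downside is that reported compliance may be slightly lower, and the 8.11 day count can no longer be compared between arms.

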8.11 Extent of Exposure

In addition, the Extent of Exposure to study treatment will be evaluated by summary statistics (N, mean, median, standard deviation) and frequencies for the “Number of Days on Therapy” by treatment group.

8.12 Data Monitoring Committee

The accruing data from patients in this trial will be monitored by an external Data Monitoring Committee (eDMC) on an ongoing basis. The composition, activities, and responsibilities of the eDMC are described in the eDMC Charter that will be provided to the eDMC are described in [Section 8.9](#).

9.0 ADHERENCE TO ETHICAL, REGULATORY, AND ADMINISTRATIVE CONSIDERATIONS

The trial must be conducted in accordance with Good Clinical Practice (GCP) as outlined in the International Conference on Harmonisation of Technical Requirements for Registration of Pharmaceuticals for Human Use (ICH) Guidelines, E6 Good Clinical Practice: Consolidated Guidance and other applicable laws and regulations. In addition, the trial must be conducted in accordance with: (i) the USA Code of Federal Regulations (CFR) if the trial is conducted under a USA IND,

regardless of the country involved; (ii) the European Union (EU) Clinical Trial Directive (CTD) and local regulations if the trial is conducted in the EU; and (iii) any specific local regulations if the trial is conducted elsewhere.

9.1 Ethical Conduct of the Trial

9.1.1 Independent Ethics Committee or Institutional Review Board

Prior to initiation of the trial at any site, the trial, including the protocol, informed consent, and other trial documents must be approved by an appropriate Institutional Review Board (IRB) or Independent Ethics Committee (IEC). The IRB/IEC must be constituted according to applicable regulatory requirements. As appropriate, amendments to the protocol must also be approved by the IRBs/IECs before implementation at the sites, unless warranted to eliminate an immediate hazard. The IRB/IEC approval should be obtained in writing, clearly identifying the trial, the documents reviewed (including informed consent), and the date of the review. The trial as described in the protocol (or amendment), informed consent, and other trial documentation may be implemented only after all the necessary approvals have been obtained and the sponsor has confirmed that it is acceptable for the investigator to do so.

In the event that the IRB/IEC requires changes in the protocol, the sponsor shall be advised and must approve the changes prior to implementation. The investigator shall not modify the trial described in the protocol once finalized and after approval by the IRB/IEC without the prior written approval of sponsor.

In countries where the investigator submits the trial protocol and statement of informed consent to the IRB/IEC, the investigator or qualified designee will forward the approvals to the sponsor.

9.1.2 Subject Information and Consent

The details of the protocol must be provided in written format and discussed with each potential subject and written informed consent must be obtained for all subjects before any trial-related procedure is performed. In obtaining informed consent, the information must be provided in language and terms understandable to the subject. The subject, or the subject's legal representative, must give their written consent to participate in the trial. The signed and dated consent form itself must be retained by the investigator as part of the trial records. A copy of the signed and dated consent form must be given to the subject. The consent form must include all of the required elements of informed consent in accordance with ICH Guidelines E6 and local laws. In addition, the sponsor specifically requests that the consent form identify it as the sponsor and state that use of the investigational product(s) is experimental and the side effects of the investigational product(s) are not completely known. The consent form must be approved by the appropriate IRB/IEC and sponsor before trial initiation at a trial site. Any subsequent changes to the approved informed consent form must

be reviewed and approved by the appropriate IRB/IEC and sponsor before implementation.

